# **Vital Signs**

The following criteria will be used, in a hierarchical sequence, to select the post-treatment measurement included in the analysis:

- If multiple vital sign measurements are obtained within the same scheduled time frame, then the measurement obtained on the time closest to the target time/day will be used;
- If more than one value meets the above criterion, then the measurement obtained on the earlier time will be used;
- If more than one value meets the above criterion, then the average value will be used.

#### 9.3 Partial Dates

The following conventions may be used for imputing partial dates for analyses requiring dates:

- For missing and partial **adverse event onset dates**, imputation will be performed using the Adverse Event Domain Requirements Specification 14
- For missing and partial **adverse event resolution dates**, imputation will be performed as follows (these conventions may change):
  - If only the day of the month is missing, the last day of the month will be used to replace the missing day
  - If the day and month are missing or a date is completely missing, it will be considered as missing.
  - In case of the date of death is present and complete, the imputed AE resolution date will be compared to the date of death. The minimum of the imputed AE resolution date and date of death will be considered as the date of AE resolution.

- Missing and partial **non-study medication domain dates** will be imputed using the derivation algorithm described in 4.3.3 of BMS Non-Study Medication Domain Requirements Specification 15
- For **death dates**, the following conventions will be used for imputing partial dates:
  - If only the day of the month is missing, the 1st of the month will be used to replace the missing day. The imputed date will be compared to the last known date alive and the maximum will be considered as the death date.
  - If the month or the year is missing, the death date will be imputed as the last known date alive.
  - If the date is completely missing but the reason for death is non-missing, the death date will be imputed as the last known date alive
- For **date of progression**, the following conventions will be used for imputing partial dates:
  - If only the day of the month is missing, the 1st of the month will be used to replace the missing day.
  - If the day and month are missing or a date is completely missing, it will be considered as missing.
  - In case of the date of death is present and complete, the imputed progression date will be compared to the date of death. The minimum of the imputed progression date and date of death will be considered as the date of progression.
- For **other partial/missing dates**, the following conventions may be used:
  - If only the day of the month is missing, the 15th of the month will be used to replace the missing day.
  - If both the day and the month are missing, "July 1" will be used to replace the missing information.
  - If a date is completely missing, it will be considered as missing.

# 9.4 Pharmacokinetic Summaries

# **In-text Tables**

For in-text pharmacokinetic tables, coefficient of variation (%CV) will be reported as integers. For other statistics except for standard deviations, values of 100 or higher will be presented as integers, values of 10 - <100 will be displayed to one decimal place, and values of 1 - < 10 will be displayed to two decimal places. Values less than 1 will be displayed to three decimal places. Ratios will also be displayed to three decimal places. Standard deviations will be reported to a precision of 1 decimal place more than the mean.

# **Handling of Non-Quantifiable Concentrations**

For the summaries of concentration-time data, concentrations that are less than the lower limit of quantification (LLOQ) should be displayed as "< LLOQ" in the listings and be treated as missing in summary tables and plots. For the purpose of calculating PK parameters, other than Ctrough, pre-dose concentrations that are less than LLOQ and concentrations prior to the first quantifiable

concentration that are less than LLOQ will be set to zero, and all other concentrations less than LLOQ will be set to missing.

Summary statistics for Ctrough concentrations will be calculated by imputing values less than LLOQ as ½ \* LLOQ. This imputation is done for Ctrough concentrations because it is treated like a PK parameter; the imputation is not done for Day 1 pre-dose concentrations. Individual Ctrough listings will display these concentrations as "< LLOQ."

All available concentration-time data and derived pharmacokinetic parameter values will be included in the PK data set and listed accordingly.

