#### **9.5 Pharmacokinetics**

Samples for PK and IMG assessments will be collected for all participants receiving BMS-986277 as monotherapy and in combination with nivolumab. PK of BMS-986277 will be characterized by noncompartmental analysis method using a validated PK analysis program. Data may be pooled with other future studies for PPK analysis of BMS-986277, the results of which will be reported in a separate pharmacometric report.

The PK parameters of BMS-986277 to be assessed following C1D1 dose administration, if data permit, include:

C max	Maximum observed blood concentration
T max	Time of maximum observed blood concentration
AUC(0-T)	Area under the blood concentration-time curve from time zero to time of last quantifiable concentration
AUC(INF)	Area under the blood concentration-time curve from time zero extrapolated to infinite time
T-HALF	Apparent terminal half-life
CLT	Total body clearance
V ss	Volume of distribution at steady-state
V z	Volume of distribution of the elimination phase

The PK parameters of BMS-986277 to be assessed following C1D15 and C1D19 doses (Part 1 monotherapy), C1D1 and C1D5 doses (Part 3 Cohort 3), and C1D1 and C1D5 doses (Part 2 and Part 3 Cohorts 1-3 BMS-986277 and nivolumab therapy), if data permit, include:

C max	Maximum observed blood concentration
T max	Time of maximum observed blood concentration

AUC(0-T)	Area under the concentration-time curve from time zero to time of last quantifiable concentration
AUC(0-48)	Area under the concentration-time curve from time zero to 48 hours postdose
AUC(0-8)	Area under the concentration-time curve from time zero to 8 hours postdose
C48	Blood concentration 48 hours postdose

In addition, the PK parameters of BMS-986277 listed below may be assessed, if data permit, following the C1D19 dose (monotherapy) and C1D5 dose (combination therapy):

CLT	Total body clearance
C ss -avg	Average blood concentration over a dosing interval at steady state (AUC[0-48]/48)
AI_AUC	AUC accumulation index; ratio of AUC(0-48) on Cycle 1 Day 19 to AUC(0-48) on Cycle 1 Day 15 for monotherapy, and ratio of AUC(0-48) on Cycle 1 Day 5 to AUC(0-48) on Cycle 1 Day 1 for combination therapy

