#### 5.2.2 Pharmacokinetics of BMS-986277

All PK analyses will be performed on the Pharmacokinetic population (described in Section 7.3). Refer to Protocol Section 9.5 for the definition of the PK parameters. The following set of pharmacokinetics endpoints will be used for BMS-986277:

- Cmax: maximum observed blood concentration
- AUC(0-T): area under the concentration-time curve from time zero to time of last quantifiable concentration
- AUC(0-8): area under the concentration-time curve from time zero to 8 hours postdose
- AUC(0-48): area under the concentration-time curve from time zero to 48 hours postdose
- AUC(INF): area under the blood concentration-time curve from time zero extrapolated to infinite time
- T-HALF: apparent terminal half-life
- CLT: total body clearance
- Vss: volume of distribution at steady-state
- Vz: volume of distribution of the elimination phase
- C48: blood concentration 48 hours postdose
- Css-avg: average blood concentration over a dosing interval at steady state
- AI AUC: AUC accumulation index
- AI Cmax: Cmax accumulation index
- THALFeff: effective elimination half-life
- Tmax: time of maximum observed blood concentration
- Ctrough: trough observed blood concentrations

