### 8.7.2 Pharmacokinetic Parameters

### **Summary:**

Summary statistics for all parameters described in Sections 5.2.2 and 5.3.3 will be tabulated for BMS-986277 and nivolumab, separately by part and dose level, where data is available.

Geometric means and coefficients of variation will be presented for Cmax, AUC(0-T), AUC(0-8), AUC(0-48), AUC(INF), CLT, Vss, Vz, C48, Css-avg, AI\_AUC, AI\_Cmax, and Ctrough. Medians and ranges will be presented for Tmax. Means and standard deviations will be presented for T-HALF and T-HALFeff.

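### SAP 9.4 handles a below-LLOQ 48-hour BMS-986277 sample inconsistently: ½ LLOQ as Ctrough, zero or missing as C48, missing in concentration tables

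*SAP*

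**What the plan says.** SAP 9.4 (Handling of Non-Quantifiable Concentrations) sets three rules.

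- **Concentration-time summaries.** Values below LLOQ are to "be treated as missing in summary tables and plots".
- **PK parameters other than Ctrough.** Zero is used for "pre-dose concentrations that are less than LLOQ and concentrations prior to the first quantifiable" concentration; "all other concentrations less than LLOQ will be set to missing".
- **Ctrough.** "Summary statistics for Ctrough concentrations will be calculated by imputing values less than LLOQ as" half of LLOQ, except for the Day 1 predose sample. The reason given is: "This imputation is done for Ctrough concentrations because it is treated like a PK parameter".

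C48 is a PK parameter in its own right. SAP 5.2.2 lists "C48: blood concentration 48 hours postdose", and Protocol 9.5 derives it after C1D15 and C1D19 in Part 1 and after C1D1 and C1D5 in Parts 2 and 3. SAP 8.7.2 states: "Geometric means and coefficients of variation will be presented for Cmax, AUC(0-T), AUC(0-8), AUC(0-48), AUC(INF), CLT, Vss, Vz, C48"; the same list goes on to Css-avg, AI_AUC, AI_Cmax and Ctrough. SAP 8.7.1 adds mean concentration profiles over time by part and dose level.

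**The concern.** After C1D15 (Part 1) and C1D1 (Parts 2-3), the sampling tables in Protocol 9.5 have no 48-hour sample except the predose sample of the next dose. One tube therefore supplies C48, Ctrough and a row of the concentration table, under different rules. A participant whose virus has fallen below LLOQ stays in the Ctrough geometric mean, drops out of the concentration table, and is either dropped from C48 or enters it as zero.

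Removing values because they are low biases what remains upward. Reported 48-hour concentration, and so apparent persistence in blood, would be too high. C48 and Ctrough could disagree for the same blood sample, and two programmers following SAP 9.4 could produce different C48 tables.

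**Working it through.** The plan states no figure to reproduce. The check traces each 48-hour sample through the rules, then sizes the bias on assumed inputs.

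**1. Which sample is the 48-hour sample** (Protocol Tables 9.5-1 to 9.5-3)

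- Part 1, after C1D15: timed samples end at 8 h; the next is C1D17 predose.
- Part 1, after C1D19: C1D21, labelled 48:00, not predose.
- Parts 2-3, after C1D1: timed samples end at 8 h; the next is C1D3 predose.
- Part 2 and Part 3 Cohorts 1-2, after C1D5: C1D7, labelled 48:00, not predose.
- Part 3 Cohort 3, after C1D5: no 48-hour sample (the next is C1D8, 72 h).

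**2. Value assigned if that sample is below LLOQ**

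| Sample | As Ctrough | As C48 | Concentration tables and plots |
|---|---|---|---|
| C1D17 or C1D3 predose | ½ LLOQ | zero if read as pre-dose, missing if read as post-dose | missing |
| C1D21 or C1D7 | not predose; the SAP does not call it a trough | missing, given an earlier quantifiable value after that dose | missing |

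The shared tube has three different values only under the zero reading, and two under the missing reading. The second row needs no choice of reading.

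**3. Parameters reached**

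- C48: directly.
- AUC(0-48): through its 48-hour point; nothing is sampled between 8 h and 48 h.
- AI_AUC, defined in Protocol 9.5 as AUC(0-48) on D19 over D15, or on D5 over D1: under the zero reading the denominator's 48-hour point is zero and the numerator's is missing.
- Css-avg = AUC(0-48)/48, assessed after C1D19 or C1D5: through the C1D21 or C1D7 sample, not the shared tube.
- Not reached: Ctrough (keeps these participants at ½ LLOQ), and Cmax and AUC(0-8) (do not use the 48-hour value).

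**4. Size, for illustration**

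Assumed: log-normal concentrations, between-participant coefficient of variation CV, share q below LLOQ. Let s = √ln(1 + CV²), z = Φ⁻¹(q), φ = the normal density at z.

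- Below-LLOQ values dropped: GM / true GM = exp[sφ/(1 − q)]
- ½ LLOQ imputed: GM / true GM = exp[sφ + q(sz − ln 2)]

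CV 100%, q = 50%: s = √ln 2 = 0.833, z = 0, φ = 0.399.

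- Dropped: exp(0.833 × 0.399 / 0.5) = exp(0.664) = 1.94
- ½ LLOQ: exp(0.332 − 0.5 × 0.693) = exp(−0.015) = 0.99

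| CV | q | Dropped | ½ LLOQ | Ratio |
|---|---|---|---|---|
| 50% | 25% | 1.22 | 0.90 | 1.35 |
| 50% | 50% | 1.46 | 0.85 | 1.71 |
| 50% | 75% | 1.82 | 0.88 | 2.08 |
| 100% | 25% | 1.42 | 0.95 | 1.49 |
| 100% | 50% | 1.94 | 0.99 | 1.97 |
| 100% | 75% | 2.88 | 1.18 | 2.44 |
| 200% | 25% | 1.71 | 1.02 | 1.68 |
| 200% | 50% | 2.75 | 1.17 | 2.35 |
| 200% | 75% | 5.02 | 1.69 | 2.97 |

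If the value is set to zero, log(0) does not exist, and the geometric mean is zero or undefined at any q above 0.

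**The case against.** **The rules differ on purpose.** Separate conventions for concentration tables, noncompartmental parameters and troughs are stated, and the Ctrough rule carries a reason. This stands as an explanation of Ctrough. But the reason is that Ctrough is treated like a PK parameter, and C48 is one by the SAP's own list, so it gives no ground for handling C48 differently.

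**The tube is only nominally at 48 hours.** Protocol 7.1.3.1 requires at least 24 h between infusions, with Days 17 and 19 within 7 days of Day 15. This is correct, and it is why the overlap is called nominal here. On the planned schedule the overlap holds.

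**The first rule covers concentration-time summaries, not parameter geometric means.** Correct. SAP 8.1 defaults to arithmetic means, with geometric means for some variables. The C48 problem comes from the second rule. Dropping low values also raises an arithmetic mean, so the mean profiles are affected too.

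**The sizes are hypothetical, and ½ LLOQ is not unbiased.** Both stand. No LLOQ, CV or below-LLOQ share is given, and the table shows ½ LLOQ erring in both directions.

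**The consequences are limited.** This stands. PK is a descriptive secondary endpoint, parameters are derived only where data permit, and the listings show values as below LLOQ. The dose-proportionality regression in SAP 8.7.2 uses Cmax, AUC(0-T) and AUC(INF), with a caution on interpretation; AUC(0-48) appears with them only in the figure list.

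**Conclusion.** The point holds, within limits. SAP 9.4 leaves C48 open between zero and missing for the tube shared with the next predose sample. It sets C48 to missing for the C1D21 and C1D7 samples, while Ctrough keeps below-LLOQ participants. Under the missing rule, C48 geometric means and late concentration summaries are biased upward; under the zero rule, the C48 geometric mean is zero or undefined. AUC(0-48), AI_AUC and Css-avg are affected only through their 48-hour point.

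The size depends on assumed inputs: about 1.9 times the true geometric mean at CV 100% with half the values below LLOQ, and 1.2 to 5.0 times across the table. The true size cannot be known from the documents.

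A reader might infer that BMS-986277 geometric means in general come only from participants with measurable virus. The documents do not support that: Ctrough includes the others, and Cmax and AUC(0-8) do not use the 48-hour value. Nor can it be said both that one tube takes three values and that C48 is restricted to measurable virus; the first needs the zero reading and the second the missing reading. A flattening of dose differences is plausible over a 100-fold dose range, but the documents give nothing from which to calculate it. DLT and ORR analyses are unaffected.

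**What to change.** Amend SAP 9.4 as follows.

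1. Apply the existing ½ LLOQ rule for Ctrough to C48, including when the 48-hour sample is the predose sample of the next dose.
2. Limit the set-to-zero rule to predose samples before the first-ever dose and to values before the first quantifiable concentration.
3. State one rule for the 48-hour point of AUC(0-48) and use it in both the numerator and the denominator of AI_AUC.
4. Print the number and percentage below LLOQ at each time point. Where more than half are below, show < LLOQ rather than a mean or median; with ½ LLOQ imputed, that median would simply be the imputed constant.

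The cost is SAP wording and minor programming, with no new samples. The drawback is that ½ LLOQ is itself approximate when most values are below LLOQ. By the same formula at 80% below (z = 0.842, φ = 0.280), it gives exp[0.233 + 0.8 × (0.701 − 0.693)] = 1.27 times the true geometric mean at CV 100%, and exp[0.355 + 0.8 × (1.068 − 0.693)] = about 1.9 times at CV 200%. Item 4 keeps such cells from being reported as a mean.

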# 10 CONTENT OF REPORTS

The complete list of analyses contributing to the clinical study report and other interim analyses will be given in the Data Presentation Plan.
